### 14.4 Device Failures, Malfunctions, and Product Nonconformities

All Trevo Retriever failures, malfunctions, and product nonconformities will be documented on the appropriate eCRF and the involved device(s) should be returned to Stryker Neurovascular for analysis if possible. Instructions for returning the study device(s) will be provided to the sites in their study binder. Device failures and malfunctions should also be documented in the subject's medical record.

All Trevo Retriever failures, malfunctions, and product nonconformities shall be reported within 24 hours of becoming aware to Stryker Neurovascular. The information can be emailed to the Stryker Neurovascular Safety Department personnel listed in the Study Contacts List.

NOTE: Trevo Retriever failures, malfunctions, and product nonconformities should be reported as soon as possible after becoming aware of them and are not to be reported as adverse events. However, if there is an adverse event that results from a device failure or malfunction, that specific event would be recorded on the appropriate eCRF. Trevo Retriever failures, malfunctions, product nonconformities and resulting AEs are reported to the Stryker Neurovascular complaint reporting system.

All Stryker Neurovascular non-study device malfunctions and nonconformities related to ancillary devices used in the procedure should be reported to the local Stryker Neurovascular customer service center. The customer service listing is provided in the study binder.

### 14.5 Reporting to Regulatory Authorities / IECs / Investigators

Stryker Neurovascular is responsible for reporting adverse event information to all participating investigators and regulatory authorities, as applicable.

The Site PI is responsible for informing Independent Ethics Committee (IEC) of UADEs and SAEs as required by local procedure. A copy of this report should be sent to Stryker Neurovascular.

**STRYKER CONFIDENTIAL** - THIS DOCUMENT CONTAINS CONFIDENTIAL AND PROPRIETARY INFORMATION THAT IS THE PROPERTY OF STRYKER CORPORATION. NEITHER THIS DOCUMENT NOR THE INFORMATION HEREIN MAY BE REPRODUCED, USED, OR DISCLOSED TO ANY THIRD PARTY WITHOUT THE PRIOR WRITTEN CONSENT OF STRYKER CORPORATION.

## Trevo® Retriever Registry (China)

### 15 Risk Benefit Analysis

The risks associated with this study are limited to a possibility that confidential patient information may be disclosed. It is possible that subjects enrolled into the Trevo Registry will receive no direct benefit from participation. Possible benefits of the registry include providing information regarding the use of the Trevo Retriever that may benefit future patients.

#### 15.1 Risk Minimization

In order to minimize risks, Stryker Neurovascular will carefully select study sites and investigators who have experience with neuro-interventional procedures. Thorough training on the protocol, IFU and registry requirements will be conducted and Stryker Neurovascular will be available to address any registry specific issues or questions. Reasonable measures will be taken to minimize any risk of loss of confidentiality including the use of subject ID numbers for data entry and de-identification of any images or records sent to the core-lab or Stryker. A Steering Committee will assist in oversight of the Trevo Registry and Safety monitoring of the data will be continuous throughout the registry.

### 16 Steering Committee

The Trevo Retriever Registry will include a Steering Committee of up to 5 members or more of which one member may assume the Trevo Registry PI role. The Steering Committee will assist in oversight of the Trevo Registry with regard to protocol review and study progress. The Steering Committee will oversee dissemination of any study results through appropriate scientific sessions and publications. One of the Steering Committee members will Chair the publication committee. Interim analyses may be conducted and published throughout the study enrollment period based on the decision of the Steering Committee. The Steering Committee may select study investigators to participate on the publication committee. The Steering/ Publication Committee will participate in the review and approval of all requests for data analyses, abstract and manuscript preparation and submission.

### 17 Ethical Considerations

#### 17.1 Compliance with Good Clinical Practices (GCP)

The Investigator will ensure that this study is conducted in accordance with the ethical principles that have their origins in the Declaration of Helsinki and that are consistent with GCP and applicable regulatory (local) requirements; whichever affords the greater protection to the subject.

#### 17.2 Independent Ethics Committee

A copy of the protocol, proposed ICF, other written subject information, and any proposed advertising material must be submitted to the IEC for written approval. A copy of the written IEC approval of the protocol and ICF must be received by Stryker Neurovascular before recruitment of subjects into the Trevo Registry. The Investigator must submit and, where necessary, obtain approval from the IEC for all subsequent protocol amendments and changes to the ICF. The Investigator must notify the IEC of SAEs per IEC procedures, UADEs occurring at the site and other SAE/UADE reports received from Stryker Neurovascular in accordance with local procedures and regulations.

**STRYKER CONFIDENTIAL - THIS DOCUMENT CONTAINS CONFIDENTIAL AND PROPRIETARY INFORMATION THAT IS THE PROPERTY OF STRYKER CORPORATION. NEITHER THIS DOCUMENT NOR THE INFORMATION HEREIN MAY BE REPRODUCED, USED, OR DISCLOSED TO ANY THIRD PARTY WITHOUT THE PRIOR WRITTEN CONSENT OF STRYKER CORPORATION.**

## **Trevo® Retriever Registry (China)**

The Investigator is responsible for obtaining initial IEC approval and renewal throughout the duration of the registry. Copies of the Investigator's reports and the IEC continuance of approval must be sent to Stryker Neurovascular.

### **17.3 Protocol Adherence**

Prior to beginning the study, the Investigator must sign the Investigator Agreement and Signature page documenting his/her agreement to conduct the study in accordance with the protocol. An Investigator must not make any changes or deviate from this protocol, except to protect the life and physical well-being of a subject in an emergency. Each deviation from the protocol may be reported to the EC per local guidelines and government regulations. Protocol deviations are defined within **Appendix B**.

Stryker Neurovascular will ensure that this study is conducted in compliance with GCPs and all applicable regulatory requirements.

## **18 Study Administration**

### **18.1 Pre-Study Documentation Requirements**

Prior to enrolling any subjects into the registry the site must complete all pre-study essential documents, and these must be confirmed to be on file with the Stryker Neurovascular, including but not limited to: CV, signed clinical trial agreement; EC approval of the study and the Informed Consent; and all required study training. A site initiation visit will be conducted prior to authorization to enroll. No site may begin enrolling subjects until they receive written approval from the Stryker Neurovascular.

### **18.2 Record Retention**

The Investigator will maintain all essential registry documents and source documentation, in original format, that support the data collected on the study subjects in compliance with the ICH/GCP guidelines. Documents must be retained for 2 years or longer per local governing Regulatory guidelines after a) the last approval of marketing application or b) formal discontinuation of the clinical investigation of the product. These documents will be retained for a longer period of time by agreement with Stryker Neurovascular or in compliance with other regulatory requirements. When these documents no longer need to be maintained, it is Stryker Neurovascular's responsibility to inform the Investigator. The Investigator will take measures to ensure that these essential documents are not accidentally damaged or destroyed. If for any reason the Investigator withdraws responsibility for maintaining these essential documents, custody must be transferred to an individual who will assume responsibility. Stryker Neurovascular must receive written notification of this custodial change.

### **18.3 Criteria for Terminating Study**

Stryker Neurovascular reserves the right to terminate the study but intends only to exercise this right for valid scientific or administrative reasons and reasons related to protection of subjects. Investigators and associated EC will be notified in writing in the event of termination.

**STRYKER CONFIDENTIAL - THIS DOCUMENT CONTAINS CONFIDENTIAL AND PROPRIETARY INFORMATION THAT IS THE PROPERTY OF STRYKER CORPORATION. NEITHER THIS DOCUMENT NOR THE INFORMATION HEREIN MAY BE REPRODUCED, USED, OR DISCLOSED TO ANY THIRD PARTY WITHOUT THE PRIOR WRITTEN CONSENT OF STRYKER CORPORATION.**

## **Trevo® Retriever Registry (China)**

### **18.4 Criteria for Suspending/Terminating a Study Center**

Stryker Neurovascular reserves the right to stop or suspend a study center at any time after the study initiation visit if no subjects have been enrolled, or if the center has multiple or severe protocol violations without justification or fails to follow remedial actions.

**STRYKER CONFIDENTIAL** - THIS DOCUMENT CONTAINS CONFIDENTIAL AND PROPRIETARY INFORMATION THAT IS THE PROPERTY OF STRYKER CORPORATION. NEITHER THIS DOCUMENT NOR THE INFORMATION HEREIN MAY BE REPRODUCED, USED, OR DISCLOSED TO ANY THIRD PARTY WITHOUT THE PRIOR WRITTEN CONSENT OF STRYKER CORPORATION.

# Trevo® Retriever Registry (China)

## 20 Appendices

### Appendix A. Abbreviations

Abbreviation/ Acronym	Full Term
AE	Adverse Event
AHA	American Heart Association
Carotid T	Distal terminus of the carotid artery
CRA	Clinical Research Associate
CRF	Case Report Form
CSA	Clinical Study Agreement
CT	Computed Tomography
CTA	Computed Tomography Angiography
DRSAE	Device-related SAE
eCRF	electronic Case Report Form
GCP	Good Clinical Practices
IA	Intra-Arterial
ICH	Intracranial Hemorrhage
ID	Identification
IFU	Instructions For Use
IV	Intravenous
IV tPA	Intravenous tissue Plasminogen Activator
LAR	Legally Authorized Representative
MR	Magnetic Resonance
MRI	Magnetic Resonance Imaging
mRS	Modified Rankin Scale
PI	Principal Investigator
SAE	Serious Adverse Event
SADE	Serious Adverse Device Effect

**STRYKER CONFIDENTIAL** - THIS DOCUMENT CONTAINS CONFIDENTIAL AND PROPRIETARY INFORMATION THAT IS THE PROPERTY OF STRYKER CORPORATION. NEITHER THIS DOCUMENT NOR THE INFORMATION HEREIN MAY BE REPRODUCED, USED, OR DISCLOSED TO ANY THIRD PARTY WITHOUT THE PRIOR WRITTEN CONSENT OF STRYKER CORPORATION.

## Trevo® Retriever Registry (China)

SAH	Subarachnoid Hemorrhage
SBP	Systolic Blood Pressure
SICH	Symptomatic Intracranial Hemorrhage
TICI	(modified) Thrombolysis in Cerebral Infarction
t-PA	Tissue Plasminogen Activator
UADE	Unanticipated Adverse Device Effect

**STRYKER CONFIDENTIAL** - THIS DOCUMENT CONTAINS CONFIDENTIAL AND PROPRIETARY INFORMATION THAT IS THE PROPERTY OF STRYKER CORPORATION. NEITHER THIS DOCUMENT NOR THE INFORMATION HEREIN MAY BE REPRODUCED, USED, OR DISCLOSED TO ANY THIRD PARTY WITHOUT THE PRIOR WRITTEN CONSENT OF STRYKER CORPORATION.

## Trevo® Retriever Registry (China)

### Appendix B. Definitions

Adverse Event (AE):	Any unintended disease or injury or untoward clinical sign in a research subject. NOTE - This definition does not imply that there is a relationship between the adverse event and the device under investigation.
Device Malfunction/Nonconformity:	The failure of a device to meet its performance specifications or otherwise perform as intended. Performance specifications include all claims made in the labeling for the device. The intended performance of a device refers to the intended use for which the device is labeled or marketed.
Embolization to New Territory:	Embolization into a previously uninvolved area of the brain, e.g. ACA embolization during MCA-M1 thrombectomy procedure.
Good Clinical Outcome:	A measure of neurologic functional outcome with a score of 0–2 on the modified Rankin Scale (mRS), usually assessed 90 days after treatment.
Irreversible Neurological Deterioration:	Neurological deterioration that is more than transitory, and is not related only to sedation. The neurological deterioration persists even after removal of sedation.
Modified Rankin Scale (mRS):	Scale for measuring the degree of disability or dependence in the daily activities of people who have suffered a stroke or other causes of neurological disability.
NIHSS Scale:	An assessment to objectively quantify the impairment caused by a stroke. It is composed of 11 items, each of which scores a specific ability between a 0 and 4. For each item, a score of 0 typically indicates normal function in that specific ability, while a higher score is indicative of some level of impairment. The individual scores from each item are summed in order to calculate a subject's total NIHSS score. The maximum possible score is 42, with the minimum score being a 0.
Pre-stroke disability:	Obtained at baseline, is representative of the subject's status before the index stroke, assessed by mRS on medical history obtained from subject, medical chart, or family members.
Protocol Deviation:	This protocol does not require specific interventions, therefore the term deviation will only be used to describe the following situation: Failure to obtain informed consent per Good Clinical Practices (GCP).
Serious Adverse Device Effect (SADE):	An adverse device effect that has resulted in any of the consequences characteristic of a serious adverse event or that might have led to any of these consequences if suitable action had not been taken or if circumstances had been less fortunate.

**STRYKER CONFIDENTIAL** - THIS DOCUMENT CONTAINS CONFIDENTIAL AND PROPRIETARY INFORMATION THAT IS THE PROPERTY OF STRYKER CORPORATION. NEITHER THIS DOCUMENT NOR THE INFORMATION HEREIN MAY BE REPRODUCED, USED, OR DISCLOSED TO ANY THIRD PARTY WITHOUT THE PRIOR WRITTEN CONSENT OF STRYKER CORPORATION.

## Trevo® Retriever Registry (China)

Serious Adverse Event (SAE):	An adverse event in a research subject that led to a death, or led to a serious deterioration in the health of the subject that resulted in a life-threatening illness or injury, or resulted in a permanent impairment of a body structure or a body function, or required in-subject hospitalization or prolongation of existing hospitalization, or resulted in medical or surgical intervention to prevent permanent impairment to body structure or a body function. SAEs are a subset of AEs.
Subarachnoid Hemorrhage (SAH):	Bleeding into the subarachnoid space - the area between the arachnoid membrane and the pia mater surrounding the brain.
Symptomatic ICH (SICH):	The primary protocol definition is adapted from ECASS III as any apparently extravascular blood in the brain or within the cranium that is associated with clinical deterioration as defined by an increase of four points or more in the NIHSS or that led to death and was judged to be the predominant cause of a neurologic deterioration. SITS-MOST definition is any PH-2, defined as dense hematoma > 30% total of the infarcted area with substantial space-occupying effect or any hemorrhage area outside the infarcted area.
Unanticipated Adverse Device Effect (UADE):	Serious adverse device effect which by its nature, incidence, severity or outcome has not been identified in the current version of the risk analysis report.

**STRYKER CONFIDENTIAL** - THIS DOCUMENT CONTAINS CONFIDENTIAL AND PROPRIETARY INFORMATION THAT IS THE PROPERTY OF STRYKER CORPORATION. NEITHER THIS DOCUMENT NOR THE INFORMATION HEREIN MAY BE REPRODUCED, USED, OR DISCLOSED TO ANY THIRD PARTY WITHOUT THE PRIOR WRITTEN CONSENT OF STRYKER CORPORATION.

# Trevo® Retriever Registry (China)

## Appendix D. Time and Events Schedule

Time and Events Schedule						
Assessments:	Pre-procedure (Screening /Baseline)	Procedure	24 (-6/+24) hrs post procedure	Discharge (or Day 5-7 whichever comes first)	Day 30 +14 days	Day 90*** ±14 days
Inclusion/Exclusion Criteria	✓					
Informed Consent*	✓					
Demographics and Medical History	✓					
Baseline Medications	✓					
Baseline Labs (PT, PTT platelets, INR, glucose). Pregnancy test, if applicable	✓					
mRS**	✓			✓	✓	✓
NIHSS assessment	✓		✓	✓		
Stroke onset/etiology	✓			✓		
CT/MR Y	✓		✓			
Angiogram Procedure Information ****Y		✓				
Hospital Stay/Discharge Disposition				✓		
Post Discharge Follow-up****					✓	✓
Adverse Events †		✓	✓	✓	✓	✓
Utilization/Economic measures ††				✓		✓
Study Completion						✓

\*Written IC must be obtained prior to any data entry.  
 \*\*Telephone mRS assessment is acceptable if subject not able to return to the clinic in person.  
 \*\*\*\*Study Staff should review the study requirements with the subject and arrange all follow-up visits at discharge.  
† All AE during procedure and only DR and PR SAE, death post procedure.  
†† De-identify forms and enter subject ID # prior to sending to Stryker  
Y CT/MR and Angiographic images will be de-identified with subject ID# if submitted to SNV or the core lab.

**STRYKER CONFIDENTIAL - THIS DOCUMENT CONTAINS CONFIDENTIAL AND PROPRIETARY INFORMATION THAT IS THE PROPERTY OF STRYKER CORPORATION. NEITHER THIS DOCUMENT NOR THE INFORMATION HEREIN MAY BE REPRODUCED, USED, OR DISCLOSED TO ANY THIRD PARTY WITHOUT THE PRIOR WRITTEN CONSENT OF STRYKER CORPORATION.**

## Trevo® Retriever Registry (China)

### Appendix E. Modified TICI Perfusion Categories

Grade 0: No Perfusion. No antegrade flow beyond the point of occlusion.

Grade 1: Penetration with Minimal Perfusion. The contrast material passes beyond the area of obstruction but fails to opacify the entire cerebral bed distal to the obstruction for the duration of the angiographic run.

Grade 2: Partial Perfusion. The contrast material passes beyond the obstruction and opacifies the arterial bed distal to the obstruction. However, the rate of entry of contrast into the vessel distal to the obstruction and/or its rate of clearance from the distal bed are perceptibly slower than its entry into and/or clearance from comparable areas not perfused by the previously occluded vessel, e.g. the opposite cerebral artery or the arterial bed proximal to the obstruction.

Grade 2a: Partial filling with <50% of the entire vascular territory is visualized.

Grade 2b: Partial filling with  $\geq 50\%$  of the entire vascular territory is visualized. If complete filling of all of the expected vascular territory is visualized, the filling is slower than normal.

Grade 3: Complete Perfusion. Antegrade flow into the bed distal to the obstruction occurs as promptly as into the obstruction and clearance of contrast material from the involved bed is as rapid as from an uninvoloved other bed of the same vessel or the opposite cerebral artery.

## Trevo® Retriever Registry (China)

### Appendix F. Modified Rankin Scale (mRS)

- 0 - No symptoms at all
- 1 - No significant disability despite symptoms; able to carry out all usual duties and activities
- 2 - Slight disability; unable to carry out all previous activities, but able to look after own affairs without assistance
- 3 - Moderate disability; requiring some help, but able to walk without assistance
- 4 - Moderately severe disability; unable to walk without assistance and unable to attend to own bodily needs without assistance
- 5 - Severe disability; bedridden, incontinent and requiring constant nursing care and attention
- 6 - Dead

## Stryker Neurovascular

**Document Title:** Trevo® Retriever Registry (China) Statistical Analysis Plan

**Document Number:** CDM10001420

# Stryker Neurovascular

**Document Title:** Trevo® Retriever Registry (China) Statistical Analysis Plan

**Document Number:** CDM10001420

**Ver AA**

## 1. Introduction

This document contains a detailed description of the Statistical Analysis Plan (SAP) for the data from the Trevo® Retriever Registry (China), coordinated with protocol of CDM 10001400.

This document provides specifications for the statistical analyses of the data to be analyzed for publications and presentations.

## 2. Study Design

This Trevo® Retriever Registry is a prospective, open-label, multi-center, international trial. The purpose of the Trevo® Registry is to assess the performance of the Trevo® retriever in real world practice to increase knowledge on the performance of the device, monitor safety outcomes, detect rare complications, and to obtain information for potential improvements for next generation devices.

### 2.1. Study Objectives

#### 2.1.1. Primary Objective

To assess real world performance of the CFDA cleared Trevo® Retriever intended to restore blood flow in the neurovasculature by removing thrombus in subjects experiencing ischemic stroke.

#### 2.1.2. Secondary Objectives

- 1) To identify optimal interventional techniques, including type of anesthesia, access, and method of clot retrieval, to result in successful outcomes.
- 2) To provide robust registry data that maybe used to support expanded indications in regulatory submissions and support reimbursement dossiers.
- 3) To gather significant amount of real-world safety data to allow further subset analyses.

### 2.2. Study Endpoints

#### 2.2.1. Primary Endpoint

The primary endpoint is revascularization status at the end of the procedure using the modified TICI scale.

#### 2.2.2. Secondary Endpoints

- 1) Day 90 mRS (good clinical outcomes defined as mRS of 0-2).
- 2) Day 90 mortality.
- 3) Neurological deterioration at 24 hours.

STRYKER CONFIDENTIAL - THIS DOCUMENT CONTAINS CONFIDENTIAL AND PROPRIETARY INFORMATION THAT IS THE PROPERTY OF STRYKER CORPORATION. NEITHER THIS DOCUMENT NOR THE INFORMATION HEREIN MAY BE REPRODUCED, USED, OR DISCLOSED TO ANY THIRD PARTY WITHOUT THE PRIOR WRITTEN CONSENT OF STRYKER CORPORATION

# Stryker Neurovascular

**Document Title:** Trevo® Retriever Registry (China) Statistical Analysis Plan

**Document Number:** CDM10001420

**Ver AA**

- 4) Rates of device and procedure related Serious Adverse Events (SAE).

## 3. Analysis Population

The Intent-to-treat principle will be followed to define the analysis population. All subjects who signed the informed consent and in whom Trevo® Retriever was deployed through the microcatheter are considered enrolled and will be included in all the analyses.

## 4. Sample Size and Power

There will be no sample size/or power estimation for this single-arm registry. Two hundred subjects will be enrolled at up to 15 centers in China.

## 5. Statistical Analysis

### 5.1. Primary Endpoint

Primary Endpoint is : Revascularization status at the end of the procedure.

The primary endpoint is measured using the modified TICI scale at the end of procedure.

Success of primary endpoint was defined as a modified TICI score of 2b or better at the end of procedure.

Primary endpoint will be analyzed by percentages, frequencies and the 95% confidence interval of the percentage of success. The 95% confidence interval will be calculated using Clopper-Pearson exact method.

### 5.2. Secondary Endpoints

#### 5.2.1. Analysis Methods

Secondary endpoints will be analyzed by percentages, and frequencies.

#### 5.2.2. Secondary Endpoints Definition

1. Day 90 mRS (good clinical outcomes defined as mRS of 0-2).
2. Day 90 mortality.

If the subjects had completed their 90-day visit, the subjects will be considered as alive at Day 90. If the subjects did not come for their Day 90 visit and died, the date of death will be used to compare with the upper window of their Day 90 (90 + 14 days post procedure). If the subjects died after the upper window of their Day 90, the subjects will be considered as alive at their Day 90. Otherwise, the subjects will be counted as death before Day 90.

3. Neurological deterioration at 24 hours which is defined as four or more points increase in the NIHSS score from the baseline to 24 hours post procedure.

STRYKER CONFIDENTIAL - THIS DOCUMENT CONTAINS CONFIDENTIAL AND PROPRIETARY INFORMATION THAT IS THE PROPERTY OF STRYKER CORPORATION. NEITHER THIS DOCUMENT NOR THE INFORMATION HEREIN MAY BE REPRODUCED, USED, OR DISCLOSED TO ANY THIRD PARTY WITHOUT THE PRIOR WRITTEN CONSENT OF STRYKER CORPORATION

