# Trevo® Retriever Registry (China)

## Protocol Synopsis

Study Objective	
Primary Objective	To assess real world performance of the Trevo® Retriever which is intended to restore blood flow in the neurovasculature by removing thrombus in subjects experiencing ischemic stroke
Primary Endpoint	Revascularization status assessment at the end of the procedure using the modified TICI score
Secondary Endpoints	
 
1. Day 90 mRS assessment
 
2. Day 90 all-cause mortality
 
3. Neurological deterioration at 24 hours post procedure, defined as a four or more point increase in the NIHSS score from the baseline score
 
4. Rates of device and procedure related serious adverse events (AEs)
 

Other Key Assessments (Data points)	
 
1. Time points will be collected on and not limited to the following: stroke symptom onset, admission to hospital/emergency department, start of Intravenous tissue Plasminogen Activator (IV tPA), angio suite arrival, arterial puncture, clot integration, Trevo removal and end of procedure (defined as the time of the final cerebral angiogram)
 
2. Data on the use of accessory products in conjunction with Trevo
 
3. Costs of hospitalization, discharge disposition
 
4. Analysis of imaging (pre, angio, post) by an independent core lab
 
5. Compare Day 90 outcome with pre-stroke mRS, baseline imaging and symptom onset to time of treatment.
 

Registry Device	Any approved Trevo Retriever approved for use by the local regulatory agency
Control	N/A
Device Sizes	All Trevo product sizes approved for use by the local regulatory agency
Study Design	
Study Design	Prospective, open-label, multi-center, China local registry
Planned Number of Subjects	200 subjects
Planned Number of Sites / Countries	Up to 15 sites
Primary Efficacy Parameter	Post-procedural Modified TICI score
Follow-Up Schedule	
 
a. Day 30 telephone contact
 
b. Day 90 clinic visit
 

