## Trevo® Retriever Registry (China)

### 8.6.2 Day 90 ( $\pm 14$ )

At Day 90 ( $\pm 14$  days) the following study assessments should be performed:

- mRS score (see **Appendix F**) - If subject is unable to return to the clinic for the Day 90 visit, a telephone mRS assessment is preferable to no assessment
- SAEs related to the device or procedure
- For all subjects who expire prior to the Day 90 assessment, available information regarding the primary cause of death and date/time of death will be recorded, as well as whether the subject was made DNR or “comfort care only” prior to expiration.

Any death or SAE must be reported to Stryker Neurovascular within 24 hours of becoming aware of the event(s).

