## 14 Adverse Events

The following adverse events will be reported:

- all adverse events that occur during the procedure
- all SAEs related to the device or the procedure through Day 90
- all serious adverse events that result in death through Day 90

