**Ver AA**

**Table 11: Secondary endpoints**

Secondary Endpoints	% of Subjects with Clinical Outcomes (n/N)*
mRS** of 0-2 at Day 90	xx.x% (xx/xxx)
Mortality rate at Day 90	xx.x% (xx/xxx)
Neurological deterioration at 24(-6/+24) hours	xx.x% (xx/xxx)
Study Device and procedure related SAE	xx.x% (xx/xxx)

\*:95% CI will be generated as needed for ad hoc analysis  
\*\*: LOCF is used for Day 90 mRS.

STRYKER CONFIDENTIAL - THIS DOCUMENT CONTAINS CONFIDENTIAL AND PROPRIETARY INFORMATION THAT IS THE PROPERTY OF STRYKER CORPORATION. NEITHER THIS DOCUMENT NOR THE INFORMATION HEREIN MAY BE REPRODUCED, USED, OR DISCLOSED TO ANY THIRD PARTY WITHOUT THE PRIOR WRITTEN CONSENT OF STRYKER CORPORATION

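### SAP 5.2.2 lets attendance at the Day 90 visit override a recorded death by Day 90, and counts some deaths on Days 91–104 as deaths before Day 90 (minor)

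*SAP*

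**What the plan says.** The Protocol Synopsis lists the endpoint as "Day 90 all-cause mortality". Protocol section 8.6.2 and Appendix D place the Day 90 visit within 14 days either side of Day 90.

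SAP 5.2.2 item 2 turns this into two tests:

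- **Attenders:** "If the subjects had completed their 90-day visit, the subjects will be considered as alive at Day 90". The day of the visit and any later death play no part.
- **Non-attenders who died:** "the date of death will be used to compare with the upper window of their Day 90 (90 + 14 days post procedure"). A later death makes the subject alive at Day 90. For any other death, "Otherwise, the subjects will be counted as death before Day 90".

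Three other places bear on which deaths are known:

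- Protocol section 14 requires reporting of "all serious adverse events that result in death through Day 90".
- Protocol section 8.6.2 asks for death details as follows: "For all subjects who expire prior to the Day 90 assessment, available information regarding the primary cause of death and date/time of death".
- Appendix D ticks "Study Completion" at the Day 90 visit and schedules no later contact.

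SAP Table 11 shows the result as a Day 90 mortality rate without qualification. Its footnote adds that "LOCF is used for Day 90 mRS".

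**The concern.** Vital status at a fixed day should follow from the date of death. Under item 2 it follows first from attendance, and then from a cut-off two weeks after the day that names the endpoint. Two subjects who die on the same day can be classified differently only because one had already been seen.

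The first test can also override data the study holds. A fatal serious adverse event on Day 85 after a Day 80 visit is reportable under Protocol section 14 and enters the SAP 5.3 summary of serious adverse events through Day 90. Table 11 would still count that subject as alive.

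At stake is the accuracy of a named secondary safety endpoint in a registry that its secondary objectives (Protocol 4.2) say may support regulatory submissions.

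**Working it through.** **1. The window.** 90 − 14 = 76 and 90 + 14 = 104. This reproduces the SAP's upper limit of Day 104.

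**2. The rule applied to test cases.**

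| Case | SAP item 2 | True status at Day 90 |
|---|---|---|
| Visit Day 80, death Day 85 | alive | dead |
| Visit Day 80, death Day 97 | alive | alive |
| No visit, death Day 85 | dead | dead |
| No visit, death Day 97 | dead | alive |
| No visit, death Day 110 | alive | alive |
| No visit, no known death | no rule given | unknown |

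The first and fourth rows are wrong. They have opposite signs.

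**3. Size: inputs.**

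- From the documents: N = 200 (SAP 4). 90-day mortality m90 = 0.20 (12/60, Protocol Table 1) or 0.33 (29/88, Protocol Table 4, Trevo arm).
- Assumed: m30 = 0.60 or 0.75 × m90, with a constant hazard h after Day 30.
- Assumed: F(t), the share of living subjects seen by Day t, is uniform on Days 76–104 or triangular with its peak at Day 90.
- Assumed: a share u of 0, 10% or 20% never attends.

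**4. Formulas.**

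- h = [ln(1 − m30) − ln(1 − m90)] / 60
- S(t) = (1 − m30) · exp(−h(t − 30))
- Wrongly alive = 200 · ∫ from 76 to 90 of h · S · F · (1 − u) dt
- Wrongly dead = 200 · ∫ from 90 to 104 of h · S · [1 − F · (1 − u)] dt
- Net change in points = (wrongly dead − wrongly alive) × 0.5, since one subject is 1/200 = 0.5 points

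Low end: m90 = 0.20, m30 = 0.75 × 0.20 = 0.15, h = (ln 0.85 − ln 0.80)/60 = 0.00101. High end: m90 = 0.33, m30 = 0.60 × 0.33 = 0.198, h = (ln 0.802 − ln 0.67)/60 = 0.00300.

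**5. Results, subjects out of 200.**

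| Never attending | Visit timing | Wrongly alive | Wrongly dead | Total | Net, points |
|---|---|---|---|---|---|
| 0 | uniform | 0.57–1.43 | 0.56–1.39 | 1.13–2.81 | −0.02 to 0.00 |
| 0 | triangular | 0.38–0.95 | 0.38–0.93 | 0.75–1.87 | −0.01 to 0.00 |
| 10% | uniform | 0.51–1.28 | 0.73–1.80 | 1.24–3.08 | +0.11 to +0.26 |
| 10% | triangular | 0.34–0.85 | 0.56–1.39 | 0.90–2.24 | +0.11 to +0.27 |
| 20% | uniform | 0.46–1.14 | 0.90–2.21 | 1.35–3.35 | +0.22 to +0.54 |
| 20% | triangular | 0.30–0.76 | 0.75–1.84 | 1.05–2.60 | +0.22 to +0.54 |

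**6. Sensitivity to the assumptions.**

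- *Earlier deaths.* With 85–90% of the 90-day deaths by Day 30, the total at full attendance is 0.3 to 1.1 subjects.
- *Visit timing.* The near-cancellation needs visits balanced around Day 90. If every visit fell on Day 76, wrongly alive = 200 × [S(76) − S(90)]. That runs from 200 × (0.8114 − 0.8000) = 2.3 to 200 × (0.6987 − 0.6700) = 5.7 subjects, or 1.1 to 2.9 points too low. If every visit fell on Day 104, wrongly dead runs from 200 × (0.8000 − 0.7888) = 2.2 to 200 × (0.6700 − 0.6425) = 5.5 subjects, or 1.1 to 2.8 points too high. The documents point to neither extreme.

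**7. Scale.** Exact (Clopper-Pearson) 95% intervals: 40/200 gives 14.7–26.2%, width 26.2 − 14.7 = 11.5 points. 66/200 gives 26.5–40.0%, width 13.5 points.

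**The case against.** The strongest defence is that Day 90 mortality here means vital status at the Day 90 assessment. Protocol 8.6.2 collects details of deaths before that assessment, and Appendix D closes the study at that visit. On this reading an attender was alive when assessed, a non-attender who died before the window closed died without being assessed, and only the label is wrong. The text does not support this. The Synopsis sets the endpoint at Day 90, Protocol section 14 collects fatal events through Day 90, and item 2 itself labels its deaths as before Day 90.

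The objection to the size has more force and stands. No passage gives the timing of deaths, so the figures in step 5 are illustrations. The model also gives a subject who has just been seen the same hazard as everyone else. If subjects close to death attend less often, fewer are wrongly alive and the two errors no longer cancel. Even so, the net change stays well inside the sampling error of a descriptive endpoint in a registry without a power calculation.

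A reader might go further, take Day 90 as the whole window to Day 104, and count every death after a completed visit as missed. The same model, with F · (1 − u) integrated from Day 76 to Day 104, gives 1.80 to 5.55 such deaths, or 0.9 to 2.8 points too low. That figure should not be held against item 2. Of these deaths, 74% (1 − 1.43/5.55) to 83% (1 − 0.38/2.25) fall after Day 90, when required death reporting has ended. Rewording the SAP cannot recover them.

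**Conclusion.** Item 2 is wrong as written for all-cause mortality at Day 90, in two ways. A completed visit on Days 76–89 overrides a recorded death by Day 90, and a non-attender's death on Days 91–104 is counted as a death before Day 90. This follows from the text alone.

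The size rests on the assumptions in step 3: about 0.8 to 3.4 of 200 subjects misclassified, and a net change of about 0 to +0.5 points. A reader might infer a materially biased mortality rate. The figures do not support that while visits are roughly balanced around Day 90. The error lies mainly in which subjects are counted as dead. The point is minor, but worth correcting because the correction is cheap.

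**What to change.** Replace item 2 with one rule for all enrolled subjects, along these lines:

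> A subject is dead at Day 90 if the recorded date of death is on or before Day 90 post procedure, whether or not the Day 90 visit was completed. A subject is alive at Day 90 if known alive on or after Day 90, or if death occurred after Day 90. A subject last seen on Days 76–89 with no death reported through Day 90 under Protocol section 14 is counted alive, and the number of such subjects is footnoted.

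In addition:

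- Show deaths recorded on Days 91–104 on a separate line labelled as deaths through Day 104 (minimum), because reporting after Day 90 is not required.
- Report the number of subjects with unknown vital status. Item 2 gives no rule for a non-attender who is not known to have died.
- For the Day 90 mRS, keep a score observed within the window. If there is no Day 90 mRS and the subject is recorded dead by Day 104, score 6 (dead in Appendix F) and carry no earlier score forward. Otherwise the LOCF footnote in Table 11 could turn a Day 30 score of 0–2 into a good outcome for a subject who died within the visit window.
- Footnote any subject whose mRS and mortality entries in Table 11 differ because of these rules. This can happen for a non-attender who dies on Days 91–104, and for a subject scored before Day 90 who then dies by Day 90.

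The cost is SAP wording, a few lines of code and a rate that may move by a fraction of a point. One limit remains: deaths between an early visit and Day 90 reach the database only through Protocol section 14 reporting. Confirmed status on Day 90 for those subjects would need an added vital-status check.
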